5.2.1.4.2 Pembrolizumab AND Cabozantinib

In situations where the attribution of toxicities in unclear, of if the toxicity is deemed to be related to both pembrolizumab and cabozantinib, follow dose modification guidelines presented in Table 5.

Table 5: Dose Modification Guidelines for Toxicities of Unclear Attribution or Deemed to be Related to Both Pembrolizumab and Cabozantinib

| Toxicity | Grade | Modification | | | | | | |
|------------------|-------|---|--|--|--|--|--|--|
| Diarrhea/Colitis | 2-3 | Hold both pembrolizumab and cabozantinib. Institute maximal anti-diarrheal therapy. Consider corticosteroids if no improvement on anti-diarrheal therapy within 24-48 hours. | | | | | | |

| | | Consider colonoscopy. | | | | | |
|----------------------------------|-------------|---|--|--|--|--|--|
| | 4 | Permanently discontinue | | | | | |
| Hypothyroidism | 2-3 | Therapy with pembrolizumab and cabozantinib can be continued while thyroid replacement therapy is instituted. | | | | | |
| | 4 | Hold pembrolizumab and cabozantinib until Grade ≤ 2 . | | | | | |
| | 2 | Hold pembrolizumab and cabozantinib until Grade ≤ 1 . | | | | | |
| AST, ALT or Increased Bilirubin | 2 | Dose reduce cabozantinib by 1 dose level for Grade ≤ 2 ALT, AST, or bilirubin lasting longer than 1 week. | | | | | |
| | 3-4 | Permanently discontinue | | | | | |
| AST, ALT AND Increased Bilirubin | 2-4 | ALT/AST elevations > 3 × ULN in combination with a bilirubin elevation > 2 × ULN require permanent treatment discontinuation. | | | | | |
| | 3 or Severe | Hold pembrolizumab and cabozantinib until Grade ≤ 1 . | | | | | |
| All Other Drug-Related Toxicity | | Permanently discontinue if G3 or severe toxicity recurs. | | | | | |
| | 4 | Permanently discontinue | | | | | |

These treatment guidelines are intended to be applied when the investigator determines the events to be related to both pembrolizumab and cabozantinib, or if the attribution is unclear. If the investigator determines the events to be related to both study drugs, these dose modifications are required. Any questions about interpretation of the dose modifications or special circumstances should be discussed with the PI.

Note: if after instituting these guidelines and after further evaluation, the event is determined to be more likely related to pembrolizumab or cabozantinib, and not both, then dose modification guidelines for either pembrolizumab (Table 3) or cabozantinib (Table 4) should be followed.

5.2.2 *Timing of Dose Administration*

Trial treatment should be administered on Day 1 of each cycle after all procedures/assessments have been completed as detailed on the Trial Schedule of Events Chart (Section 6.0). Trial treatment may be administered up to 3 days before or after the scheduled Day 1 of each cycle due to administrative reasons.

All trial treatments will be administered on an outpatient basis.

Pembrolizumab 200 mg will be administered as a 30 minute IV infusion every 3 weeks. Every effort should be made to target infusion timing to be as close to 30 minutes as possible. However, given the variability of infusion pumps from site to site, a window of -5 minutes and +10 minutes is permitted (i.e., infusion time is 30 minutes: $-5 \min/+10 \min$).

The Pharmacy Manual contains specific instructions for the preparation of the pembrolizumab infusion fluid and administration of infusion solution.

Cabozantinib will be obtained commercially. Subjects will be given oral and/or written instructions on dose to be taken by the investigator or by properly trained staff designee. Subjects will receive a medication diary with written dosing instructions and be asked to record the time and date they take each dose. Subjects will be instructed to bring their medication diary to each study visit for assessment of compliance.

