5.2.1.3 Pembrolizumab

Adverse events (both non-serious and serious) associated with pembrolizumab exposure may represent an immunologic etiology. These adverse events may occur shortly after the first dose or several months after the last dose of treatment.

There will be no dose modification of pembrolizumab, which is to be administered at a fixed dose of 200 mg IV every 21 days. A window of +/- 3 days is allowed for administrative/ scheduling reasons.

Pembrolizumab must be withheld for drug-related toxicities and severe or life-threatening AEs as per Table 3 below. See Section 5.4 for supportive care guidelines, including use of corticosteroids.

Table 3: Dose Modification and Toxicity Management Guidelines for Immune-related AEs Associated with Pembrolizumab General instructions:

- 1. Severe and life-threatening irAEs should be treated with IV corticosteroids followed by oral steroids. Other immunosuppressive treatment should begin if the irAEs are not controlled by corticosteroids.
- 2. Study intervention must be permanently discontinued if the irAE does not resolve or the corticosteroid dose is not $\leq 10 \text{ mg/day}$ within 12 weeks of the last study intervention treatment.
- **3.** The corticosteroid taper should begin when the irAE is \leq Grade 1 and continue at least 4 weeks.
- **4.** If study intervention has been withheld, study intervention may resume after the irAE decreased to \leq Grade 1 after corticosteroid taper.

| Immune-related AEs | Toxicity grade or conditions (CTCAEv4.0) | Action taken to pembrolizumab | irAE management with corticosteroid and/or other therapies | Monitor and follow-up |
|-----------------------|---|--|--|---|
| Pneumonitis | Grade 2 Grade 3 or 4, or recurrent Grade 2 | Withhold Permanently discontinue | Administer corticosteroids (initial dose of 1-2 mg/kg prednisone or equivalent) followed by taper Add prophylactic antibiotics for opportunistic infections | Monitor participants for signs and symptoms of pneumonitis Evaluate participants with suspected pneumonitis with radiographic imaging and initiate corticosteroid treatment |

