| Nephritis: grading according to increased creatinine or acute kidney injury | Grade 2 Grade 3 or 4 | Withhold Permanently discontinue | • Administer corticosteroids (prednisone 1-2 mg/kg or equivalent) followed by taper. | Monitor changes of renal function |
|---|---|--|--|--|
| Neurological Toxicities | Grade 2 Grade 3 or 4 | Withhold Permanently discontinue | Based on severity of AE administer corticosteroids | • Ensure adequate evaluation to confirm etiology and/or exclude other causes |
| Myocarditis | Grade 1 Grade 2-4 | Withhold Permanently discontinue | Based on severity of AE administer corticosteroids | • Ensure adequate evaluation to confirm etiology and/or exclude other causes |
| Exfoliative Dermatologic Conditions | Suspected Stevens- Johnson Syndrome (SJS), toxic epidermal necrolysis (TEN), or Drug Rash with Eosinophilia and Systemic Symptom (DRESS) | Withhold | Based on severity of AE administer corticosteroids | • Ensure adequate evaluation to confirm etiology and/or exclude other causes |
| | Confirmed SJS, TEN, or DRESS | Permanently discontinue | | |

| All other immune- related AEs | Persistent Grade 2 | Withhold | • Based on type and severity of AE administer corticosteroids | • Ensure adequate evaluation to confirm etiology and/or exclude other causes | | | | | |
|--|---|---|--|--|--|--|--|--|--|
| | Grade 3 | Withhold or | | | | | | | |
| | | discontinue based | | | | | | | |
| | | on the type of | | | | | | | |
| | | event ^e | | | | | | | |
| | Grade 4 or | Permanently | | | | | | | |
| | recurrent | discontinue | | | | | | | |
| | Grade 3 | | | | | | | | |
| Note: Non-irAE will | Note: Non-irAE will be managed as appropriate, following clinical practice recommendations. | | | | | | | | |
| ^a AST/ALT: >3.0 to bilirubin:>1.5 to 3 | 5.0 x ULN if baseline .0 x ULN if baseline | ne normal; >3.0 to 5.0 x e normal; >1.5 to 3.0 x l | baseline, if baseline abnormal; baseline if baseline abnormal | | | | | | |
| ^b AST/ALT: >5.0 to 10.0 x baseline if t | in:>3.0 to 10.0 x ULN if baseline normal; >3.0 to | | | | | | | | |
| c AST/ALT: >20.0 x bilirubin: >10.0 x | ^c AST/ALT: >20.0 x ULN, if baseline normal; >20.0 x baseline, if baseline abnormal; bilirubin: >10.0 x ULN if baseline normal; >10.0 x baseline if baseline abnormal | | | | | | | | |

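### For a first Grade 3 pneumonitis, nephritis, neurological toxicity or myocarditis judged related to both drugs, Tables 3 and 5 give different pembrolizumab instructions and no precedence is stated

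*Combined protocol and SAP*

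**What the plan says.** Section 5.2.1.3 introduces Table 3 with a mandatory sentence: "Pembrolizumab must be withheld for drug-related toxicities and severe or life-threatening AEs as per Table 3 below". It makes no exception for events to which cabozantinib may also have contributed. The rows that matter include "Pneumonitis | Grade 2 Grade 3 or 4, or recurrent Grade 2 | Withhold Permanently discontinue", "Nephritis: grading according to increased creatinine or acute kidney injury | Grade 2 Grade 3 or 4 | Withhold Permanently discontinue" and "Myocarditis | Grade 1 Grade 2-4 | Withhold Permanently discontinue". In each, the first grade listed pairs with withholding and the second with a permanent stop. The neurological row follows the nephritis pattern.

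Section 5.2.1.4.2 sets the scope of Table 5: "In situations where the attribution of toxicities in unclear, of if the toxicity is deemed to be related to both pembrolizumab and cabozantinib". For events judged related to both drugs its force is explicit: "If the investigator determines the events to be related to both study drugs, these dose modifications are required". For unclear attribution the text only directs the investigator to follow the table.

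Table 5 has its own rows for diarrhea/colitis, hypothyroidism and liver tests. Everything else falls to a catch-all row for other drug-related toxicity. That row begins at Grade 3 or severe, where both drugs are held until Grade 1 or lower, and adds "Permanently discontinue if G3 or severe toxicity recurs". At Grade 4 it requires a permanent stop. A closing note sends the reader back to Table 3 or Table 4 only when further evaluation points to one drug rather than both.

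**The concern.** An event related to both drugs is, on ordinary reading, still related to pembrolizumab. Both mandatory sentences then apply to it, and for some serious immune events they lead to different actions. Two investigators following the protocol faithfully could manage the same Grade 3 event differently: one stops pembrolizumab permanently, the other holds it and may resume.

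This is first a patient-safety matter. It also affects what the SAP will summarise. Section 8.2.2 reports exposure and lists adverse events leading to discontinuation, and both would depend partly on which table each investigator used.

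**Working it through.** No computed figure is involved. The check sets the pembrolizumab action in Table 3 beside that in Table 5, grade by grade, and then asks whether any sentence decides between them.

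| Event and grade | Table 3 | Table 5 | Comparison |
|---|---|---|---|
| Pneumonitis, first Grade 3 | Permanent stop | Hold to Grade 1 or lower; stop on recurrence | Conflict |
| Nephritis, first Grade 3 | Permanent stop | As above | Conflict |
| Neurological, first Grade 3 | Permanent stop | As above | Conflict |
| Myocarditis, first Grade 3 | Permanent stop | As above | Conflict |
| Pneumonitis, Grade 2 | Withhold | No entry | Gap |
| Pneumonitis, recurrent Grade 2 | Permanent stop | No entry | Gap |
| Nephritis, Grade 2 | Withhold | No entry | Gap |
| Neurological, Grade 2 | Withhold | No entry | Gap |
| Myocarditis, Grade 1 | Withhold | No entry | Gap |
| Myocarditis, Grade 2 | Permanent stop | No entry | Gap |
| Diarrhea/colitis, recurrent Grade 3 | Permanent stop | Grade 2-3 hold, no recurrence rule | Differs |
| All four named events, Grade 4 | Permanent stop | Permanent stop | Same |
| Liver tests, Grade 2 and Grade 3-4 | Withhold; permanent stop | Hold; permanent stop, plus a stop for ALT/AST above 3 × ULN with bilirubin above 2 × ULN | Table 5 equal or stricter |
| Hypothyroidism, Grade 4 | Continue | Hold to Grade 2 or lower | Table 5 stricter |
| Hyperthyroidism or hypophysitis, Grade 4 | Withhold or stop, at discretion | Permanent stop (catch-all row) | Table 5 stricter |

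The count is four direct conflicts, six gaps and one missing recurrence rule.

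Next, is there a tie-breaker?

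- The mandatory sentence in 5.2.1.3 speaks of withholding, but it does so by reference to Table 3, whose action column gives a permanent stop at these grades.
- The note closing 5.2.1.4.2 returns to Table 3 only once one drug is thought responsible, so an event still attributed to both stays under Table 5.
- Section 5.2.1.2 permits modifying one drug independently for events attributed to that drug alone. It does not address shared events.
- Section 5.2.1.4.2 refers questions of interpretation to the principal investigator, which is a route for asking and not a rule.

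None of these says that Table 3 ceases to apply to an immune event of shared attribution, or which table prevails where they differ.

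**The case against.** The strongest reply is that the protocol already routes by attribution: Table 3 for pembrolizumab, Table 4 for cabozantinib, Table 5 for shared or unclear cause. On that reading only one table applies at a time, there is no literal contradiction, and different actions by attribution are a design choice. This is a fair reading of the table titles and the closing note. But the mandatory sentence in 5.2.1.3 is not limited to events due to pembrolizumab alone. Even if routing is accepted, adding cabozantinib as a contributor changes a first Grade 3 stop into a hold with possible resumption, and the protocol gives no reason for this.

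Section 5.2.1.2 also lets investigators interrupt either drug for adverse events at their discretion. That permits a hold; it does not settle a stated permanent stop.

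Frequency is a further point. The cabozantinib profile in Section 5.4.2 does not list pneumonitis, myocarditis or nephritis, so shared attribution of those may be uncommon. It does list reversible posterior leukoencephalopathy, so neurological overlap is possible. The documents give no rate.

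Several stronger readings are tempting and are not supported:

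- A reader might infer that Table 5 is looser throughout. The comparison shows it equal or stricter in several rows.
- A reader might infer that both tables are mandatory when the cause is unclear. The stronger wording covers only events judged related to both drugs.
- A reader might infer that Table 5 cancels the Grade 1-2 actions. It is silent there and nowhere says to continue, so these are gaps and not opposing instructions.
- A reader might infer that the Grade 3 conflict disturbs Phase I evaluability. Under Section 2.1.2, a likely related Grade 3 non-hematologic, non-hepatic event in the window is generally a DLT whichever drug is blamed, and none of the four is a named exception. Section 2.1.1 makes subjects non-evaluable only for holds unrelated to a DLT. A lower-grade hold could matter, but no such effect has been shown.

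**Conclusion.** The point holds in bounded form. For a first Grade 3 occurrence of four serious immune event types judged related to both drugs, two binding provisions prescribe different pembrolizumab actions and the protocol does not rank them. Six lower-grade points and recurrent Grade 3 diarrhea/colitis are left incomplete in Table 5. For unclear attribution the same divergence arises from an instruction to follow Table 5, with less force.

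The conflict rests on reading 5.2.1.3 as covering any pembrolizumab-related event, including one shared with cabozantinib. On the narrower routing reading it becomes an unexplained dependence on the attribution call, which still needs stating plainly. How many patients would be affected cannot be estimated from the documents. No effect on the response-rate test or its error rates is claimed. Because permanent discontinuation for serious events is at issue and the remedy is cheap, it should be corrected.

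**What to change.** Reconcile Section 5.2.1.3 (Table 3 and its footnotes) with Section 5.2.1.4.2 (Table 5 and the text beneath it). State in both sections which table governs pembrolizumab when an immune-related event is attributed to both drugs, and when its attribution is unclear. Make that statement cover the grades at which Table 5 has no entry and recurrent Grade 3 diarrhea/colitis. Which action applies is for the sponsor to decide. This review takes no position on it, and does not ask that attribution cease to matter.

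The cost is a text amendment to two sections, with the IRB review that Section 10.7 requires of any amendment. It adds no procedures, visits or patients.

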5.2.3 Trial Blinding/Masking and Treatment Allocation

This is an open-label trial; therefore, the investigator and subject will know the treatment administered. This is a single arm, open-label study. All subjects will receive the combination of pembrolizumab and cabozantinib.

5.3 Concomitant Medications/Vaccinations (allowed & prohibited)

Medications or vaccinations specifically prohibited in the exclusion criteria are not allowed during the ongoing trial. One exception is the use of corticosteroids during the study to treat an immune-mediated adverse event, as noted in Section 5.2.1.3, Table 3, and Section 5.4.1. If there is a clinical indication for one of these or other medications or vaccinations specifically prohibited during the trial, discontinuation from trial therapy or vaccination may be required. The final decision on any supportive therapy or vaccination rests with the investigator and/or the subject's primary physician.

5.3.1 Acceptable Concomitant Medications

All treatments that the investigator considers necessary for a subject's welfare may be administered at the discretion of the investigator in keeping with the community standards of medical care. All concomitant medication should be recorded in the subject research chart including all prescription, over-the-counter (OTC), herbal supplements, and IV medications.

All concomitant medications received within 28 days before the first dose of trial treatment and 30 days after the last dose of trial treatment should be recorded. Concomitant medications administered after 30 days after the last dose of trial treatment should be recorded for SAEs and Events of Clinical Interest (ECIs) as defined in Section 7.4.

5.3.2 Prohibited Concomitant Medications and Therapies

Subjects are prohibited from receiving the following therapies during the Screening and Treatment Phase of this trial:

- Antineoplastic systemic chemotherapy or biological therapy
- Immunotherapy not specified in this protocol
- Chemotherapy not specified in this protocol
- Investigational agents other than pembrolizumab and cabozantinib
- Radiation therapy to a target lesion
 - Note: Palliative radiation therapy to a symptomatic non-target lesion, including the brain, may be allowed at the investigator's discretion.
- Live vaccines within 30 days prior to the first dose of trial treatment and while participating in the trial. Examples of live vaccines include, but are not limited to, the following: measles, mumps, rubella, varicella/zoster, yellow fever, rabies, BCG, and typhoid vaccine.
- Systemic glucocorticoids for any purpose other than to modulate symptoms from an event of clinical interest of suspected immunologic etiology should be first discussed with and approved by the Principal Investigator.
 - Additionally, the use of physiologic doses of corticosteroids may be approved after consultation with the Principal Investigator.

The Exclusion Criteria describes other medications that are prohibited in this trial.

5.4 Rescue Medications & Supportive Care

5.4.1 Supportive Care Guidelines for Pembrolizumab-Related Toxicities

Subjects should receive appropriate supportive care measures as deemed necessary by the treating investigator. Suggested supportive care measures for the management of adverse events with potential immunologic etiology are outlined below. Where appropriate, these guidelines include the use of oral or intravenous treatment with corticosteroids as well as additional anti-inflammatory agents if symptoms do not improve with administration of corticosteroids. Note that several courses of steroid tapering may be necessary as symptoms may worsen when the steroid dose is decreased. For each disorder, attempts should be made to rule out other causes such as metastatic disease or bacterial or viral infection, which might require additional supportive care. The treatment guidelines are intended to be applied when

the investigator determines the events to be related to pembrolizumab.

Note: if after the evaluation, the event is determined not to be related to pembrolizumab, the investigator does not need to follow the treatment guidance (as outlined below). Refer to Section 5.2.1 for dose modification.

It may be necessary to perform conditional procedures such as bronchoscopy, endoscopy, skin biopsy, or skin photography as part of evaluation of the event.

- Pneumonitis:
 - For **Grade 2 events**, treat with systemic corticosteroids. When symptoms improve to Grade 1 or less, steroid taper should be started and continued over no less than 4 weeks.
 - For **Grade 3-4 events**, immediately treat with intravenous steroids. Administer additional anti-inflammatory measures, as needed.
 - Add prophylactic antibiotics for opportunistic infections in the case of prolonged steroid administration.

• Diarrhea/Colitis:

Subjects should be carefully monitored for signs and symptoms of enterocolitis (such as diarrhea, abdominal pain, blood or mucus in stool, with or without fever) and of bowel perforation (such as peritoneal signs and ileus).

- All subjects who experience diarrhea/colitis should be advised to drink liberal quantities of clear fluids. If sufficient oral fluid intake is not feasible, fluid and electrolytes should be substituted via IV infusion. For Grade 2 or higher diarrhea, consider GI consultation and endoscopy to confirm or rule out colitis.
- For Grade 2 diarrhea/colitis, administer oral corticosteroids.
- For Grade 3 or 4 diarrhea/colitis, treat with intravenous steroids followed by high dose oral steroids.
- When symptoms improve to Grade 1 or less, steroid taper should be started and continued over no less than 4 weeks.

• Type 1 diabetes mellitus (if new onset, including diabetic ketoacidosis [DKA]) or

≥ Grade 3 Hyperglycemia, if associated with ketosis (ketonuria) or metabolic acidosis (DKA)

- For T1DM or Grade 3-4 Hyperglycemia
 - Insulin replacement therapy is recommended for Type I diabetes mellitus and for Grade 3-4 hyperglycemia associated with metabolic acidosis or ketonuria.
 - Evaluate subjects with serum glucose and a metabolic panel, urine ketones, glycosylated hemoglobin, and C-peptide.

• Hypophysitis:

- For **Grade 2** events, treat with corticosteroids. When symptoms improve to Grade 1 or less, steroid taper should be started and continued over no less than 4 weeks. Replacement of appropriate hormones may be required as the steroid dose is tapered.
- For **Grade 3-4** events, treat with an initial dose of IV corticosteroids followed by oral corticosteroids. When symptoms improve to Grade 1 or less, steroid taper should be started and continued over no less than 4 weeks. Replacement of appropriate hormones may be required as the steroid dose is tapered.

• Hyperthyroidism or Hypothyroidism:

Thyroid disorders can occur at any time during treatment. Monitor subjects for changes in thyroid function (at the start of treatment, periodically during treatment, and as indicated based on clinical evaluation) and for clinical signs and symptoms of thyroid disorders.

- Grade 2 hyperthyroidism events (and Grade 2-4 hypothyroidism):
 - In hyperthyroidism, non-selective beta-blockers (e.g. propranolol) are suggested as initial therapy.
 - In hypothyroidism, thyroid hormone replacement therapy, with levothyroxine or liothyroinine, is indicated per standard of care.
- Grade 3-4 hyperthyroidism
 - Treat with an initial dose of IV corticosteroid followed by oral corticosteroids. When symptoms improve to Grade 1 or less, steroid taper should be started and continued over no less than 4 weeks.

Replacement of appropriate hormones may be required as the steroid dose is tapered.

- Hepatic:
 - For **Grade 2** events, monitor liver function tests more frequently until returned to baseline values (consider weekly).
 - Treat with IV or oral corticosteroids
 - For Grade 3-4 events, treat with intravenous corticosteroids for 24 to 48 hours.
 - When symptoms improve to Grade 1 or less, a steroid taper should be started and continued over no less than 4 weeks.
- Renal Failure or Nephritis:
 - For Grade 2 events, treat with corticosteroids.
 - For Grade 3-4 events, treat with systemic corticosteroids.
 - When symptoms improve to Grade 1 or less, steroid taper should be started and continued over no less than 4 weeks.
- Management of Infusion Reactions: Signs and symptoms usually develop during or shortly after drug infusion and generally resolve completely within 24 hours of completion of infusion.

Table 6 below shows treatment guidelines for subjects who experience an infusion reaction associated with administration of pembrolizumab (MK-3475).

| NCI CTCAE Grade | Treatment | Premedication at subsequent dosing |
|--|--|---|
| Grade 1 Mild reaction; infusion | Increase monitoring of vital signs as medically indicated until the subject is deemed medically stable in the opinion of the | None |
| interruption not indicated; intervention not indicated | investigator. | |
| Grade 2 Requires infusion interruption but responds promptly to symptomatic treatment (e.g., antihistamines, NSAIDS, narcotics, IV fluids); prophylactic medications indicated for <=24 hrs | Stop Infusion and monitor symptoms. Additional appropriate medical therapy may include but is not limited to: IV fluids Antihistamines NSAIDS Acetaminophen Narcotics Increase monitoring of vital signs as medically indicated until the subject is deemed medically stable in the opinion of the investigator. If symptoms resolve within one hour of stopping drug infusion, the infusion may be restarted at 50% of the original infusion rate (e.g., from 100 mL/hr to 50 mL/hr). Otherwise dosing will be held until symptoms resolve and the subject should be premedicated for the next scheduled dose. Subjects who develop Grade 2 toxicity despite adequate premedication should be permanently discontinued from further trial treatment administration. | Subjectmaybepremedicated1.5h(± 30minutes)prior to infusionofpembrolizumab(MK-3475)with:Diphenhydramine50 mgpo(or equivalent dose of antihistamine).Acetaminophen500-1000mgpo(or equivalent dose of antipyretic). |

Table 6: Infusion Reaction Treatment Guidelines

| NCI CTCAE Grade | Treatment | Premedication at subsequent dosing |
|--|--|---------------------------------------|
| Grades 3 or 4 Grade 3: Prolonged (i.e., not rapidly responsive to symptomatic medication and/or brief interruption of infusion); recurrence of symptoms following initial improvement; hospitalization indicated for other clinical sequelae (e.g., renal impairment, pulmonary infiltrates) Grade 4: Life-threatening; pressor or ventilatory support indicated | Stop Infusion. Additional appropriate medical therapy may include but is not limited to: IV fluids Antihistamines NSAIDS Acetaminophen Narcotics Oxygen Pressors Corticosteroids Epinephrine Increase monitoring of vital signs as medically indicated until the subject is deemed medically stable in the opinion of the investigator. Hospitalization may be indicated. Subject is permanently discontinued from further trial treatment administration. | No subsequent dosing |
| Appropriate resuscitation equipment administration. | t should be available in the room and a physician readily available | during the period of drug |

